10.2. Treatment Compliance

The Investigator will record the presumed dose of the study drug and the dates of the initial and final administration for each dose.

Compliance must be monitored closely and determined at each visit. Compliance will be assessed by counting capsules and dividing the actual number of doses taken (per capsule count) by the number of doses the subject should have taken within a visit period and multiplying by 100. All subjects will be reminded of the importance of strict compliance with taking study drug for the effectiveness of treatment and for the successful outcome of the study. Subjects who miss more than 25% of scheduled doses or take more than 125% of the scheduled doses will be considered noncompliant. Evidence of noncompliance must be immediately reported to the Clinical Research Associate (CRA) and/or Medical Monitor.

10.3. Concomitant Medications

The following information on all medication administered between screening and study follow-up or at discontinuation will be recorded on the CRF: Medication name, dose, frequency, route, start date, stop date, indication, and whether the medication was started after last dose of study medication.

Information on the format and version of coding dictionary is provided in the Data Management Plan (DMP). All medications will be coded using World Health Organization – Drug Dictionary (WHO-DD).

Collection of prior and concomitant medication review is described in Section 11.2.

10.3.1. Prior Medications

Subjects taking nonpsychotropic medications must be on a stable dose within 30 days prior to screening and maintain the dose and regimen throughout the study.

Subjects must maintain their anti-Parkinson's medications on a stable dose throughout the study. Dose adjustments will not be allowed, unless approved by the medical monitor.

Prior treatment with antipsychotic agents (including pimavanserin) must be discontinued within 5 half-lives prior to randomization. Prior treatment with centrally acting anticholinergic agents including but not limited to diphenhydramine, trihexyphenidyl, and biperidin must be discontinued no less than two weeks prior to randomization. Antipsychotic and centrally acting anticholinergic medications are prohibited during the course of the study.

Use of antidepressant, anxiolytic, and sleep medications is allowed. The dose of these medications must be a stable dose within 30 days prior to screening and be maintained throughout the study.

Use of acetylcholinesterase inhibitors, such as donepezil, rivastigmine, and galantamine is allowed but the dose of these medications must be stable for at least 30 days prior to screening and must be maintained throughout the study.

The addition of antipsychotic agents, central acting anti-cholinergic agents, including but not limited to diphenhydramine, trihexyphenidyl, and biperiden, antidepressants, hypnotics or any other aids used for sleep is prohibited.

Medications for the treatment of anxiety/agitation such as lorezapam up to a dose of 6 mg/day or its equivalent are permitted with prior authorization from the medical monitor and should not be used within 8 hours prior to efficacy assessments.

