Subjects who provided written informed consent to participate in the study will be evaluated for eligibility during a screening/washout period of up to 14 days, during which they will be tapered off all antipsychotic or centrally acting anticholinergic medications in a manner that is consistent with labeling recommendations and conventional medical practices. The subject's caregiver must also provide consent for the subject to participate in this study as well as consent for collection of caregiver data as related to the assessment of the subject's neuropsychiatric status measured by the NPI. The screening visit may occur over more than one day. The washout period can start immediately at screening. Prior treatment with antipsychotic agents must be discontinued at least 5 half-lives prior to the site performing the NPI and MMSE screening assessments.

Subjects who meet the study entry criteria at screening (see inclusion criteria in the full protocol in Section 8.1) and have gone through the washout period, as necessary, will enter the 6-week double-blind treatment period.

Double-blind Treatment Period (6 weeks):

Randomization/Treatment:

[figure not shown]
At Baseline (Day 1, Visit 3), subjects who have successfully completed screening/washout will be randomly assigned via interactive voice/web response system (IXRS) in a 2:1 ratio to SEP-363856 or placebo. Study drug dosing will begin following completion of the baseline assessments on the same day (Day 1, Visit 3). Double-blind study drug will be taken in-clinic at the Baseline visit (Day 1) and on visit days when subject titrates up. Subsequent doses starting the following day should be taken at bedtime. For the remainder of the study, subjects will take one capsule of study drug per day at approximately the same time each evening at bedtime. After receiving the initial dose (Day 1) and after each up-titration subjects will remain in the clinic for 2 hours of clinical observation; which will include assessments of orthostatic vital signs (1 hour [± 15 min] and 2 hours [± 15 min] post dose), additional medical assessments can be performed as needed per investigator discretion. Findings will be collected on appropriate case report forms (CRFs). Subjects will be discharged home if medically stable. Dosing will continue once daily (QD) at bedtime for the remainder of the study, without regard for food.

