Investigational Product, Dosage and Mode of Administration:

SEP-363856 treatment will be size #0, Swedish-orange capsules (25 mg, 50 mg or 75 mg) administered orally once daily (QD). Study drug may be taken without regard for food at approximately the same time each evening before bedtime.

During the double-blind treatment period all subjects randomized to SEP-363856 will be flexibly dosed at 25, 50, or 75 mg/day.

During the open-label treatment period all subjects will receive SEP-363856 flexibly dosed at 25, 50 or 75 mg/day.

Duration of Treatment: 6 weeks for DB period, 12 weeks for open-label

Reference Therapy, Dosage and Mode of Administration:

During the double-blind treatment period, matching placebo size #0, Swedish-orange capsules administered orally once daily. Study drug may be taken without regard for food at approximately the same time each evening before bedtime.

Subjects randomized to placebo will receive placebo during the double-blind treatment period.

Concomitant Medications:

Subjects taking nonpsychotropic medications must be on a stable dose within 30 days prior to screening, and maintain the dose and regimen throughout the study.

Subjects must maintain their anti-Parkinson's medications on a stable dose throughout the study. Dose adjustments must be approved by the medical monitor.

Prior treatment with antipsychotic agents (including pimavanserin) must be discontinued at least 5 half-lives prior to randomization. Prior treatment with centrally acting anticholinergic agents including but not limited to diphenhydramine, trihexyphenidyl, and biperidin must be discontinued no less than two weeks prior to randomization. Antipsychotic and centrally acting anticholinergic medications are prohibited during the course of the study.

Use of antidepressant, anxiolytic, and sleep medications is allowed. The dose of these medications must be a stable dose within 30 days prior to screening and be maintained throughout the study.

Medications for the treatment of anxiety/agitation such as lorezapam up to a dose of 6 mg/day or its equivalent are permitted with prior authorization from the Medical Monitor and should not be used within 8 hours prior to efficacy assessments.

See Section 10.3 of full protocol for full description of concomitant medications and restrictions.

Study Endpoints:

Primary Endpoint:

The primary endpoint is the change from double-blind Baseline in total SAPS-PD score at Week 6.

Secondary Endpoints:

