¹ BMI will be calculated by site staff using an equation for BMI at Screening only. BMI for all other visits will be derived within the Electronic Data Capture (EDC) system.

^m Screening assessments must be performed after washout.

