Subjects who meet the study entry criteria at screening (see inclusion criteria in Section 8.1) and have gone through the washout period, as necessary, will enter the 6-week double-blind treatment period.

Double-blind Treatment Period (6 weeks):

Randomization/Treatment:

[figure not shown]
At Baseline (Day 1, Visit 3), subjects who have successfully completed screening/washout (see randomization criteria in Section 8.3) will be randomly assigned via interactive voice/web response system (IXRS) in a 2:1 ratio to SEP-363856 or placebo. Study drug dosing will begin following completion of the baseline assessments on the same day (Day 1, Visit 3). Double-blind study drug will be taken in-clinic at the Baseline visit (Day 1) and on visit days when subject titrates up. Subsequent doses starting the following day should be taken at bedtime. For the remainder of the study, subjects will take one capsule of study drug per day at approximately the same time each evening at bed-time. After receiving the initial dose (Day 1) and after each up-titration, subjects will remain in the clinic for 2 hours of clinical observation, which will include assessments of orthostatic vital signs (1 hour [± 15 min] and 2 hours [± 15 min] post dose), additional medical assessments can be performed as needed per investigator discretion. Findings will be collected on appropriate case report forms (CRFs). Subjects will be discharged home if medically stable. Dosing will continue QD at bedtime for the remainder of the study, without regard for food.

Subjects will have clinic visits and procedures as outlined in Table 2. Telephone calls to the subjects will be made on the first 2 days after a dose adjustment. An unscheduled visit will be made as early as possible for dose adjustments or evaluation of safety/tolerability issues. Efforts will be made to ensure that the subject's caregiver remains the same for all study visits. All post-Baseline clinic visits will have a window of \pm 2 days relative to the date of the Baseline visit (Visit 3).

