11.9.1. Screening/Washout: Visit 1 (Day -14 to -1)

A unique screening number will be assigned to each subject.

Subjects who fail screening, may be re-screened up to 2 times, if judged appropriate by the Investigator. Re-screened subjects will be re-consented and all Visit 1 procedures will be repeated. A new unique screening number will be assigned to each re-screened subject.

The subject's eligibility assessment will be reviewed by the contract research organization's (CRO) oversight quality team along with the sponsor based on protocol specified inclusion and exclusion criteria. The sponsor will participate in the eligibility review process with the CRO to ascertain the subject's eligibility and will be copied on all communications between the CRO and the site relating to eligibility. In the event the CRO/sponsor and site do not agree on a subject's eligibility then the subject will not be enrolled.

Subjects will be evaluated at the screening visit (1 to 14 days before the baseline visit) to determine their eligibility for the study. This visit may occur over more than one day. The following procedures will be conducted during this visit:

- Obtain signed informed consent and privacy authorization from the subject and caregiver before conducting any other visit procedures.
- Review inclusion and exclusion criteria
- Obtain demographic information
- Prior/concomitant medications
- Medical history
- Psychiatric history/mental status
- Physical and neurological examination

- Height and weight; clinical site staff to calculate and record BMI
- Vital sign measurements (prior to ECG)
- Perform ECG
- Blood samples for clinical laboratory evaluation (hematology, serum chemistry, serum prolactin, glycosylated hemoglobin [HbA_{1c}], glucose panel, lipid panel, thyroid panel, and coagulation panel)
- For female subjects, blood samples for serum human chorionic gonadotropin (β-hCG) and serum follicle stimulating hormone (FSH)
- Urine sample for urinalysis and urine drug screen (UDS)
- NPI, must be performed after washout
- MMSE, must be performed after washout
- C-SSRS
- Pretreatment events

11.9.2. **Baseline: Visit 3 (Day 1)**

The following procedures will be conducted predose during this visit:

- Prior/concomitant medications
- Physical and neurological examination
- Vital sign measurements (prior to ECG)
- Weight
- Perform standard 12-lead ECG.
- Review inclusion and exclusion criteria

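### Protocol Section 10.3.1 words the antipsychotic washout as a maximum interval (within 5 half-lives), where the rest of the protocol sets a minimum (at least 5 half-lives).

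*Protocol*

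**What the plan says.** The antipsychotic washout rule is stated with its length in four places in the protocol.

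- **Section 10.3.1, Prior Medications:** prior antipsychotics, including pimavanserin, "must be discontinued within 5 half-lives prior to randomization".
- **Synopsis, Concomitant Medications:** the corresponding sentence, with the same reference point, says they "must be discontinued at least 5 half-lives prior to randomization".
- **Synopsis, Screening/Washout Period, and Section 7.1:** both say prior antipsychotics "must be discontinued at least 5 half-lives prior to the site performing the NPI and MMSE screening assessments".

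The sentence that follows the rule in Section 10.3.1 covers centrally acting anticholinergics, which "must be discontinued no less than two weeks prior to randomization". The section then adds: "Antipsychotic and centrally acting anticholinergic medications are prohibited during the course of the study".

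Other parts of the protocol require washout without giving its length. The Visit 1 checklist in Section 11.9.1 has the entry "NPI, must be performed after washout", with a matching entry for the MMSE. Section 7.1 restricts randomization to "subjects who have successfully completed screening/washout". A footnote to the schedule of assessments states: "Screening assessments must be performed after washout".

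**The concern.** Stopping a drug is a single act. An instruction to stop it within a given time before randomization therefore reads as an upper limit on how long ago the last dose may have been. That is the reverse of a washout. Taken literally, it admits a subject who stopped the day before and rules out one who stopped long ago.

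The place of the error matters. The synopsis refers readers to Section 10.3 for the full account of medication restrictions, Section 11.2 does the same, and exclusion criterion 28 defines disallowed medications by reference to it. A coordinator who follows those references reaches the faulty sentence.

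At stake is an antipsychotic-free screening and baseline. The NPI entry threshold must be met at Visit 1 and Visit 3, and the first SAPS-PD is at Visit 3. If washout were incomplete, eligibility and the baseline of the primary endpoint could be measured with prior drug still present.

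**Working it through.** The plan has no figure of its own to reproduce here. The check compares the statements of the rule, followed by a small illustration.

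**1. The four statements side by side**

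| Place in the protocol | Direction | Counted back from |
|---|---|---|
| Synopsis, Screening/Washout Period | minimum | screening NPI and MMSE |
| Synopsis, Concomitant Medications | minimum | randomization |
| Section 7.1 | minimum | screening NPI and MMSE |
| Section 10.3.1 | literally a maximum | randomization |

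Three of four are minimums. The synopsis screening text is the counterpart of Section 7.1, so these are not three independent confirmations. The closest comparison is the synopsis Concomitant Medications sentence, which has the same subject and reference point and differs in direction.

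**2. The two reference points.** Screening NPI and MMSE come before randomization. A subject with 5 half-lives off drug before those assessments also has at least 5 before randomization. The reference points are nested and do not contradict each other; Section 10.3.1 simply gives the less strict one.

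**3. How the section uses *within*.** Elsewhere in Section 10.3.1 the word describes a continuing state (a stable dose over the 30 days before screening) or a period in which a drug is not to be taken (8 hours before efficacy assessments). The anticholinergic washout, which is the parallel rule, is worded as an explicit minimum.

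**4. What the two readings allow.** Assume first-order elimination, so the fraction left after n half-lives is 0.5^n.

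- At least 5 half-lives: at most 0.5^5 = 0.03125, or 3.1%, remains.
- Literal Section 10.3.1: any n from 0 to 5, so between 0.5^5 = 3.1% and 0.5^0 = 100% remains.
- The two rules are both met only at exactly n = 5.

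**5. Whether the minimum is a practical constraint.** Section 4.1 says pimavanserin takes 10 to 14 days of daily dosing to reach steady state. Assume that this corresponds to 4 to 5 half-lives.

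- Shortest half-life: 10 / 5 = 2 days, so 5 half-lives = 10 days.
- Longest half-life: 14 / 4 = 3.5 days, so 5 half-lives = 17.5 days.

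The screening/washout period is at most 14 days. On this assumption, a subject stopping pimavanserin at screening would need most or all of that period, or slightly more. Sites then have reason to look up the exact minimum.

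**The case against.** The strongest reply is that *within* need not mean a maximum. *Discontinued* can describe the state of being off drug, and the sentence then says the subject must be off drug throughout the last 5 half-lives, which is a minimum. The stable-dose sentences in the same section use the word in that way. The literal maximum is also clinically absurd, so a site is unlikely to act on it. This reading is possible, but it is strained next to an adjacent rule written as an explicit minimum and a synopsis counterpart that says *at least*.

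The second reply is that the risk is already controlled. Section 7.1 sets the stricter minimum. The Visit 1 checklist puts NPI and MMSE after washout. Randomization requires completed washout. Section 11.2 has sites record all past and current antipsychotics. The CRO and sponsor review each subject's eligibility. All of this stands and makes harm unlikely. However, the checklist and the randomization text do not say how long washout is, and the eligibility review applies inclusion and exclusion criteria, none of which states the 5 half-life figure. These safeguards reduce the risk without correcting the sentence. The schedule footnote is weaker support, because in the text as extracted its marker sits on the Visit 8 entries. The Visit 1 checklist is the better reference.

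The third reply is that no consequence is shown. That is correct. Residual drug at baseline predates randomization and would not differ systematically by arm.

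**Conclusion.** The concern holds. Section 10.3.1 misstates an eligibility-related rule that the protocol states correctly in three other places, and it does so in the section that sites are told to consult. The intended rule is a minimum of 5 half-lives, and a drafting error is the most likely explanation.

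The consequence is limited to a site that applies Section 10.3.1 alone and assesses eligibility or baseline before washout is complete. Such a subject could have more than 3.1% of the prior drug remaining, assuming first-order elimination. The documents give neither the share of subjects who need washout nor the effect of residual drug on SAPS-PD, so nothing beyond that can be sized. Sample size, power and type I error are unaffected. The sentence should be corrected, but it does not call the design into question.

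**What to change.** In Section 10.3.1, replace *within* with *at least*. That one word removes the conflict.

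In the same edit, count the interval back from the screening NPI and MMSE, as Section 7.1 does, so that the sentence reads that prior antipsychotics "must be discontinued at least 5 half-lives prior to the site performing the NPI and MMSE screening assessments". This is the stricter reference point, and meeting it also meets the randomization one.

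The cost is a wording correction to one sentence. If the reference point is changed as well, the Concomitant Medications sentence in the synopsis should be edited to match. The design, sample size and analysis do not change.

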10.3.2. Rescue Medication

Antipsychotic medication will not be allowed during the course of study. Antianxiety medication to treat agitation and anxiety is permitted with prior authorization from the Medical Monitor.

10.3.3. Restricted Therapies

Subjects will be allowed to continue with ongoing physical or occupational therapy initiated prior to screening which aims to address their physical disabilities. No new therapies should be initiated during the course of the study.

10.4. Other Restrictions

Subjects should abstain from alcohol from screening through the end of the study.

10.5. Description of Study Periods

10.5.1. Description of Study Periods

The periods of the study, their duration, and subject status are provided below in Table 7.

Table 7: Description of Study Periods

Study Period	Visit Number	Study Day ^a (OL Study Day)	Inpatient/Outpatient
Screening	Visit 1	-14 to -1 (NA)	Outpatient
Double-blind Baseline	Visit 3	1 (NA)	Outpatient
Double-blind	Visit 4	8 (± 2 days) (NA)	Outpatient
Double-blind	Visit 5	15 (± 2 days) (NA)	Outpatient
Double-blind	Visit 6	29 (± 2 days) (NA)	Outpatient
Double-blind End/ Open-label baseline	Visit 7	43 (± 2 days) (OL Day 1)	Outpatient
Open-label Extension	Visit 8	50 (± 2 days) (OL Day 8)	Outpatient
Open-label Extension	Visit 9	57 (± 2 days) (OL Day 15)	Outpatient
Open-label Extension	Visit 10	64 (± 2 days) (OL Day 22)	Outpatient
Open-label Extension	Visit 11	71 (± 3 days) (OL Day 29)	Outpatient
Open-label Extension	Visit 12	99 (± 3 days) (OL Day 57)	Outpatient
Open-label Extension	Visit 13 / EOT / ET	127 (± 3 days) (OL Day 85)	Outpatient
Follow-up	Visit 14	7 days after last dose (± 2 days)	Outpatient

^a Study Day is based on Visit 3 (Day 1) and OL Day is based on Visit 7 (Study Day 43).

10.6. Guidance for Overdose

Potential overdose to SEP-363856 has not been evaluated. Appropriate supportive measures should be instituted and close medical supervision and monitoring should continue until the subject recovers. Consider the possibility of multiple-drug overdose.

11. STUDY ASSESSMENTS

A study schematic is presented in Figure 1. Summary of assessments to be conducted at each visit for the DB treatment period and OL extension are presented in Table 2 and Table 3, respectively.

Efforts will be made to ensure that the subject's caregiver remains the same caregiver for all study visits. For this study a caregiver should be involved in the daily care of the subject and have detailed knowledge of the subject's behavior.

The same study site rater should perform the same scale assessment(s) for a given subject, whenever possible.

All post-Baseline DB treatment visits will have a window of \pm 2 days relative to the date of the Baseline visit (Visit 3).

The SAPS-PD, CGI-S, MMSE, UPDRS II, UPDRS III, and neurological exam should be performed during the subject's on-periods (ie, at a time when the subject shows no clinical evidence of worsening in their Parkinson's symptoms, as determined by the site investigator). The NPI is administered to the caregiver only and should be completed referencing the subject's on-period.

For this study 1 week is defined as 7 days and 1 month is defined as 4 weeks (28 days).

